- Participants with mCRPC for whom secondary hormonal manipulation has failed. Up to 45% of patients develop resistance to novel hormone therapy within 6-9 months of treatment due to mutations in the androgen receptor (eg, AR-V7). In addition, for approximately one third of these patients, a new phenotype emerges with highly aggressive small cell-like/undifferentiated neuroendocrine features. Patients resistant to novel hormone therapy such as abiraterone and/or enzalutamide have a very poor outcome due to the absence of therapeutic alternatives. The PrCa VBIR may offer these patients a therapy that is anticipated to have few anti-androgen side effects; would delay disease progression; reduce the need for chemotherapy; and may prolong survival.
- Participants with hormone sensitive prostate cancer following definitive local therapy, who were determined to have rising prostate specific antigen (PSA) at a rate putting them at high risk for rapid development of metastatic disease (defined by a PSA doubling time <10 months). Although there is no worldwide standard-of-care in this population, Androgen Deprivation Therapy (ADT) is frequently used when the PSA rises rapidly in the apparent disease-free setting (termed “Biochemical Relapse, or BCR”). The use of androgen deprivation impacts significantly the quality-of-life (QoL) of these patients. For example, sexual/hormonal dysfunction is a significant concern for many patients considering the duration of androgen deprivation, (24 – 36 months), and its significant side effects of muscle wasting, fatigue, and reduction in libido. In this setting patients whose disease is BCR may benefit from a therapy with few androgen side effects, such as PrCa VBIR. In patients with BCR, the goal will be to prevent or delay the need for chemical castration, preserve the QoL of the patients, and ultimately delay progression to metastatic disease.

Part B, the Dose Expansion phase of the study, will evaluate participants with metastatic castrate resistant prostate cancer (mCRPC) whose disease has progressed despite novel hormonal treatment (enzalutamide or abiraterone) irrespective of the time of administration of these anti-androgen agents. Additionally, participants with biochemical relapse of disease (BCR), meaning there is no detectable metastatic disease, are included in Part B.

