#### **4.2. Exclusion Criteria for all Participants**

Participants with any of the following characteristics/conditions will not be included in the study:

1. Diagnosis of neuroendocrine prostate tumor or neuroendocrine tumor component.
2. Metastases to the brain or liver.
3. ECOG performance status (PS)  $\geq 2$ .
4. History of prior malignancy other than prostate cancer within the past 3 years excluding successfully resected basal cell carcinoma or squamous cell carcinoma of the skin.
5. Major surgery within 4 weeks of first dose.
6. Radiation therapy within 4 weeks of starting study treatment, except: palliative or focal/limited radiotherapy to a limited field is allowed after consultation with the sponsor's medical monitor at any time during study participation, including during screening.
7. Systemic anti-cancer therapy (including immunotherapy and chemotherapy) within 4 weeks or 5 half-lives, whichever is shorter, prior to first dose.
8. Sepuleucel-t and Prostvac within 12 months of first dose.
9. Receipt of an investigational agent within 30 days, prior to first dose.

10. Receipt of an immunosuppressive dose of corticosteroids or other immunosuppressive medication (eg, methotrexate, rapamycin) within 30 days of first dose. (Exceptions: Participants with adrenal insufficiency may take up to 5 mg of prednisone or equivalent daily. Topical, nasal and inhaled corticosteroids are allowed).
11. History of or active autoimmune disorders (including but not limited to: myasthenia gravis, thyroiditis, pneumonitis, rheumatoid arthritis, multiple sclerosis, systemic lupus erythematosus, scleroderma).
12. Acetylcholine receptor binding antibody  $\geq 0.5$  nmol/L and/or abnormal neurologic examination at screening indicating possible underlying myasthenia gravis.
13. History of inflammatory bowel disease (eg, Crohn's disease or ulcerative colitis), celiac disease, acute or chronic colitis, or other chronic gastrointestinal conditions associated with diarrhea.

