PSA, PSA velocity, PSA slope and PSA doubling time (PSADT); PSA will be provided from laboratory data. PSA velocity is defined as the slope of the linear regression line of PSA against time in month. PSA slope is the slope of the linear regression line of natural log of PSA against time in month. PSA doubling time is defined as the natural log of 2 divided by the slope of the linear regression line of the natural log of PSA against time in month (see 10.2). These analyses will be conducted both for Central PSA and Local PSA in separate tables. PSA kinetics will be presented at individual level by timepoint (listings and plots). Mean % and absolute change from baseline in PSA kinetics may be presented by cohort. To report PSA-based outcomes, PCWG3 recommends that the percentage of change in PSA from baseline, as well as the maximum decline in PSA, PSA velocity, PSADT and PSA slope that occurs at any point after treatment be reported for each patient using a waterfall plot. Waterfall plots provide a broader and more sensitive display of data, and are more informative until a validated surrogate of clinical benefit is available.

A PSA-50 response rate may be calculated by cohort. PSA-50 response rate is defined as the proportion of patients whose on-study PSA declined from baseline by at least 50% at two consecutive measurements at least 3 weeks apart, prior to other systematic anti-cancer therapy. For the subset of PSA-50 responders, a duration of PSA-50 response will be summarized. Duration of PSA-50 response is defined as the period between the first

measurement when PSA-50 response was achieved to the measurement when PSA-50 response no longer holds.

Swimmer plots may be used to display duration of treatment and PSA values at each applicable time point.

CTC

The frequency of “traditional” and “all candidate” CTCs in whole blood each expressed as CTC/mL will be assessed in pre treatment (Screening, Cycle 1 Day 1) and post treatment (eg. Cycle 1 Day 71, Cycle 2 Day 1, Cycle 2 Day 29, Cycle 2 Day 99, and End of Treatment) samples. Analysis of the CTC endpoints may include absolute CTC and fold-change from baseline (pretreatment) by patient and % change and mean fold-change by cohort.

MDSC

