10.4. Appendix: Immune-related Response Criteria per RECIST 1.1 (irRECIST)

Immune-related progressive disease (irPD) needs to be confirmed by a second, consecutive assessment at least 4 weeks apart. irPD is also considered to be confirmed if the patient:

- dies within 12 weeks after the initial observation of irPD, or
- discontinues treatment due to disease progression (clinical deterioration without radiological documentation) prior to or within 12 weeks after the assessment of irPD.

Immune-related Best Overall Response (irBOR) will be derived based on reported lesion responses at different evaluation time points from the start date until confirmed immune-related disease progression per irRECIST, according to the following rules.

[figure not shown]
- Confirmed irCR = at least two determinations of irCR at least 4 weeks apart before irPD.
- Unconfirmed irCR = one determination of irCR before irPD (and not qualifying for confirmed irCR or irPR).
- Confirmed irPR = at least two determinations of irPR or better at least 4 weeks apart before irPD (and not qualifying for confirmed irCR).
- Unconfirmed irPR = one determination of irPR before irPD (and not qualifying for confirmed irCR or irPR or unconfirmed irCR).
- irSD = at least one irSD or irPD assessment ≥ 6 weeks after start date and before confirmed irPD (and not qualifying for confirmed/unconfirmed irCR or irPR).
- irPD = ≤ 12 weeks after the first dose of study treatment and at least two consecutive determinations of irPD at least 4 weeks apart. irPD is also considered to be confirmed if the patient:
 - dies within 12 weeks after the initial observation of irPD, or
 - discontinues treatment due to disease progression (clinical deterioration without radiological documentation) prior to or within 12 weeks after the assessment of irPD.
- NE: All other cases.

Only tumor assessments performed before the start of any further anti-cancer treatment will be considered in the assessment of irBOR.

Immune-related Objective Response (irOR) is defined as irCR or irPR according to irRECIST from start date until confirmed irPD or death due to any cause. Both irCR and irPR must be confirmed by repeat assessments performed no less than 4 weeks after the criteria for immune-related response are first met. Also, irPD must be confirmed by a

second, consecutive assessment at least 4 weeks apart. Immune-related OR rate (irORR) is the proportion of patients with irOR in the analysis set.

CCI

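### PSA waterfalls, kinetics summaries and PSA-50 duration state no cut at new anti-cancer therapy, so PSA falls from ADT started in follow-up can appear as the best decline

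*SAP*

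**What the plan says.** SAP 8.1.3 (PSA kinetics) describes four PSA outputs.

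- **Waterfalls.** Citing PCWG3, it calls for the percentage change from baseline and the "maximum decline in PSA, PSA velocity, PSADT and PSA slope that occurs at any point after treatment be reported for each patient". This is the only window given for these displays.
- **Cohort kinetics.** "Mean % and absolute change from baseline in PSA kinetics may be presented by cohort", with no window stated. SAP Appendix 10.2 gives definitions and a worked example but no window either.
- **PSA-50 response.** A fall of at least half from baseline "at two consecutive measurements at least 3 weeks apart, prior to other systematic anti-cancer therapy".
- **PSA-50 duration.** It runs from the first "measurement when PSA-50 response was achieved to the measurement when PSA-50 response no longer holds", with no mention of other therapy.

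Elsewhere the SAP does stop at new therapy. Appendix 10.4 says "Only tumor assessments performed before the start of any further anti-cancer treatment will be considered in the assessment of irBOR", and its Table 2 censors irPFS and irDR at new anti-cancer therapy. SAP 8.1.2 keeps only safety data from before new systemic therapy.

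Protocol 1.2 says of biochemical relapse that "Androgen Deprivation Therapy (ADT) is frequently used when the PSA rises rapidly". Protocol 4.1.1 (criteria 10 and 13) requires these participants to be hormone sensitive and not on ADT. Protocol 5.7.2 bars other anti-tumor treatment during study treatment, and Protocol 6.3 adds 6 months of follow-up afterwards. Exclusion 6 in Protocol 4.2 says "palliative or focal/limited radiotherapy to a limited field is allowed" at any time during participation, after consultation with the medical monitor.

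**The concern.** If the text is programmed as written, a participant whose PSA rises on study treatment, who stops and then starts ADT, contributes his post-ADT value to the waterfall. For maximum decline, a later value can only leave the bar unchanged or deepen it. The same values enter the regressions behind velocity, slope and PSADT, and they can prolong a PSA-50 response that began before ADT.

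This matters most in Cohorts 1B and 5B. In SAP 6.5 the ORR, irRECIST, bone and rPFS endpoints are restricted to Cohort 3B, so PSA is the visible anti-tumor measure for biochemical relapse. These cohorts have no control arm, and Protocol 3.5 bases the recommended Phase 2 dose on evidence that includes efficacy.

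**Working it through.** **1. Windows side by side (visible text)**

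| Output | Stated stop |
|---|---|
| PSA waterfalls | none (any point after treatment) |
| Cohort PSA kinetics | none |
| PSA-50 duration | loss of response only |
| PSA-50 response | other systemic therapy |
| Safety data | new systemic therapy |
| irBOR, irPFS, irDR | new anti-cancer therapy |

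**2. How a post-ADT value can arise.** New ADT is barred during study treatment, so the route runs through the 6-month follow-up. The protocol expects new therapy in that period: its AE footnotes shorten AE follow-up if another anticancer therapy starts, and Protocol 8.2 ends non-serious AE reporting at that point. Cohort 3B participants are already castrate (Protocol 4.1.2), so the ADT route concerns 1B and 5B. Whether PSA is drawn in follow-up cannot be seen because the schedule is redacted.

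**3. Reproducing the SAP example (Appendix 10.2).** PSA is 0.5, 1, 0.6, 1 and 1.6 at calendar months t = 0, 1, 2, 3 and 5.

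- Mean t = 2.2, and the sum of (t − 2.2)² = 14.8.
- Slope of ln PSA = 2.943/14.8 = 0.199; PSADT = ln 2/0.1989 = 3.49 months.
- Velocity = 2.86/14.8 = 0.193.

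The SAP states 0.20, 3.49 months and 0.19, so the example is reproduced. With months of 30.4375 days the results are 0.198, 3.49 and 0.193. That scale is used below.

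**4. Adding post-therapy values.** Assumptions: the first value is baseline; two further readings follow 2 and 4 months after the last; each lies a fixed percentage below the last value of 1.6. Best change = lowest later value/0.5 − 1.

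| Assumed fall | Added values | Slope | PSADT (months) | Velocity | Best change |
|---|---|---|---|---|---|
| cut applied | none | 0.198 | 3.49 | 0.193 | +20% |
| 30% | 1.12 | 0.079 | 8.8 | 0.067 | +20% |
| 50% | 0.80 | 0.036 | 19.4 | 0.026 | +20% |
| 80% | 0.32 | −0.081 | −8.6 | −0.035 | −36% |
| 90% | 0.16 | −0.169 | −4.1 | −0.055 | −68% |

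A bar of −50% needs a value of 0.25, a fall of 1 − 0.25/1.6 = 84% from the last reading. In the 90% row the waterfall shows a decline of more than half for a man whom the PSA-50 definition would not count if the fall followed ADT.

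**5. Effect on a cohort.** Each participant whose bar moves this way changes the share with a deep decline by 1/n: 1/20 = 5.0 points in 1B and 1/15 = 6.7 points in 5B. Three would change it by 15.0 and 20.0 points.

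**The case against.** The best defence is that the one PSA response rate is already protected. ADT is systemic, and PSA-50 response counts only declines "prior to other systematic anti-cancer therapy". That stands: a reader might infer that ADT inflates the PSA-50 rate, and the definition rules this out.

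Other points also stand in part.

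- **Direction.** A reader might infer that the error always favours activity. For maximum decline it cannot go the other way. For PSADT it can: a negative slope gives a negative doubling time, which pulls a cohort mean down.
- **Visibility.** The PSA schedule and SAP 8.1.4 are redacted, so a cut could be stated where it cannot be read. Individual listings and plots by timepoint, and possible swimmer plots, would let a careful reader spot late values. They do not correct the waterfall.
- **Comparison with imaging.** The SAP is not uniform. RECIST 1.1 best overall response states no new-therapy cut in 8.1.3, but it is limited to treatment and maintenance assessments, when other anti-tumor treatment is barred.
- **Status.** The SAP plans no hypothesis tests, and the cohort kinetics and PSA-50 rate are optional. The waterfall sentence reports a recommendation. Even so, it is the only window given, so a programmer would follow it.
- **Radiotherapy.** The PSA-50 cut is systemic only, so permitted limited-field radiotherapy falls outside it. A reader might infer that such radiotherapy will create PSA-50 responders. The documents do not show this: 1B and 5B participants have no metastatic involvement on imaging at entry, and nothing indicates how often radiotherapy would give a confirmed 50% fall in 3B.

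**Conclusion.** The point holds for the waterfalls, the cohort kinetics and PSA-50 duration. The visible SAP text allows PSA values after new systemic therapy into all three, out of line with its own rules for PSA-50 response, irBOR, irPFS, irDR and safety. In 1B and 5B, a fall caused by ADT started in follow-up can be displayed as the best decline or can distort the kinetics.

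The 5.0 and 6.7 points are the effect of one participant on the share with a deep decline in the waterfall. A reader might take them as an estimate of bias; they are not, because the number affected is unknown and may be zero. The post-therapy readings in the working are also assumed. Radiotherapy is a secondary gap, correct on the text but of unknown effect.

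**What to change.** In SAP 8.1.3, state one window: maximum PSA decline, PSA velocity, PSA slope, PSADT and their cohort summaries are derived only from PSA values before the start of any further systemic anti-cancer therapy, including ADT. Duration of PSA-50 response is censored at the last PSA before that start. Later values stay in the listings, flagged.

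Secondarily, flag PSA values taken after any on-study radiotherapy and present PSA-50 with and without them. Excluding them outright is more debatable, since it would also discard values after purely palliative treatment. Exclusion 6 in Protocol 4.2 and Protocol 5.7.2 must be reconciled on radiotherapy during study treatment.

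The cost is a few sentences and one date filter. Protocol 5.7 already has concomitant treatments and non-drug interventions recorded on the CRF until the end of study visit. Post-therapy values leave the summaries but remain in the listings.

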15. **Registration:** Participant number and dose level allocation operated by Pfizer Inc.
16. **Investigational Product Administration:** Treatment to be administered after all other assessments required on that day have been performed.
17. **Tumor Assessments:** Tumor assessments will include all known or suspected disease sites. Screening images may be obtained within 5 weeks of registration. Imaging obtained as part of standard of care but within 28 days (-7 days) of registration may be used for screening assessment. Imaging may include chest, abdomen and pelvis CT or MRI scans or bone scans. Bone scans will be performed at baseline if disease is suspected and on-study as appropriate to follow disease. Baseline central nervous system (CNS) imaging is not required with the exception of symptomatic participants to rule out CNS metastases. CT or MRI scans, as well as bone scans, when indicated, are to be done every 8 weeks ( $\pm$ 5 days) with the first one to occur 8 weeks after C1D1 until disease progression that requires new treatment modality, permanent discontinuation, or death. Disease progression will be confirmed with two consecutive timepoints at least 4-6 weeks apart in the absence of rapid clinical deterioration. Tumor assessment should be repeated at the End of Treatment visit if more than 6 weeks have passed since the last evaluation. CCI [REDACTED]  
[REDACTED]
19. **Acetylcholine receptor (AChR) antibody:** Sample to be sent to the central laboratory for analysis. CCI [REDACTED] Treatment decisions will be made based on the clinical diagnosis.
20. **Circulating Tumor Cells:** Approximately 10 mL of blood will be collected for evaluation of circulating tumor cells by the central laboratory.
21. **Serology:** Approximately 10 mL of blood will be collected for central evaluation of IgG antibody responses against the vaccine.
22. **Peripheral Blood Mononuclear Cells:** Approximately 50 mL of blood will be collected for central evaluation of immune response. In addition, the samples may also be used for T cell receptor (TCR) sequencing analysis.
23. **Myeloid Derived Suppressor Cells:** Approximately 5 mL of blood will be collected for central evaluation of circulating MDSC.

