#### **4.1.1. Additional Inclusion Criteria for Participants with Rising PSA at High Risk for Recurrence After Definitive Local Therapy (Biochemical Relapse)**

9. Definitive loco-regional therapy for primary diagnosis including one of the following:
  - a. External radiotherapy or any salvage therapy including but not limited to brachytherapy, cryotherapy or salvage therapy;
  - b. Radical prostatectomy and radiotherapy therapy, such as external radiotherapy or brachytherapy;

- c. Prostatectomy only for participants who are not candidates for salvage therapy. Salvage therapy includes but is not limited to any of the following: any radiation therapy (such as external beam therapy, brachytherapy) or any other salvage therapy such as cryotherapy.

10. Hormone sensitive (androgen dependent) relapsing prostate cancer post definitive local therapy. Relapse is defined as a subsequent detectable PSA ( $\geq 0.2$  ng/ml) that increases on 2 or more determinations after radical prostatectomy. The values must be separated by at least 2 weeks.
11. High risk of development of metastatic disease defined as PSA doubling time less than or equal to 10 months (calculated at least 3 months before treatment administration). The PSADT calculation must include all available PSA values available over the past 6 months prior to registration using the Memorial Sloan Kettering Cancer Center (MSKCC) PSA Doubling Time Prediction Tool available at the following website: <http://nomograms.mskcc.org/Prostate/PsaDoublingTime.aspx>.
12. Male participants able to father children must agree to use one highly effective method of contraception throughout the study and for at least 90 days after the last dose of assigned treatment.
13. No concurrent use of ADT or orchiectomy. Prior use of ADT in the neoadjuvant or adjuvant setting with radiotherapy is allowed as long as it was completed at least 6 months prior to registration.
14. No evidence by imaging (of any type) of metastatic involvement as follows: loco-regional or distant lymph nodes; loco-regional or distant soft tissues; or any organ involvement, including bone.
15. Testosterone level  $\geq 150$  ng/dL.

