7. HANDLING OF MISSING VALUES

CCI

All the safety, immune responses, pharmacokinetic, pharmacodynamics, and immunogenicity analyses and summaries will be based on data as observed and no explicit imputation will be applied.

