7.2. Immune Responses Lower Limit of Quantitation

Titers below the assay detection limit will be assigned a value of one-half that limit.

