The percentage of MDSCs will be assessed in pretreatment (Screening, Cycle 1 Day 1) and post treatment samples. MDSC levels will be presented per patient and per cohort by GMTs and GMFRs. Analyses of MDSC endpoints may include absolute and fold-change from baseline (pretreatment) by patient and % change and mean fold-change by cohort.

Bone scan assessment

Given the frequency of bone involvement in patients with progressive, castration-resistant disease, the decreased emphasis of early changes in PSA, and the increased availability of cytostatic agents, reliable methods to assess changes in bone are of increasing importance. PCWG3 recognizes that standards for using MRI and PET to assess bone metastases are under active investigation, so only radionuclide bone scans are considered here. PCWG3 also recognizes that there are no validated criteria for response on radionuclide bone scan.

[figure not shown]
For control/relieve/eliminate end points, the PCWG3 recommends that post-treatment changes be recorded simply as either “no new lesions” or “new lesions.” However, progression at the first scheduled assessment should be confirmed on a second scan performed 6 or more weeks later, in the absence of clearly worsening disease or disease-related symptoms. In the event of visible lesions disappearing, this should also be confirmed at the next scheduled assessment.

For prevent/delay end points, progressing disease on bone scan is considered when a minimum of two new lesions is observed. PCWG3 does not recommend performing a follow-up bone scan before 12 weeks of treatment unless clinically indicated. At the first 12-week reassessment, defining disease progression requires a confirmatory scan (which shows additional new lesions compared with the first follow-up scan) performed 6 or more weeks later, because lesions visible at the first 12-week assessment may represent disease that was not detected on the pretreatment scan. When further progression is documented on the confirmatory scan, the date of progression recorded for the trial, is the date of the first scan that shows the change.

Correlative analyses

Plots may be generated to display PSA kinetics vs. PSA antibodies (serology: Luminex assay). Similar plots may be generated to evaluate individual patient trends on MDSC, CTC and T-cell response.

CCI

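### The optional mean fold-change and patient-level % change in circulating tumor cells are undefined for a zero baseline, and in the remaining participants the mean ratio departs from 1 with no treatment effect

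*SAP*

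**What the plan says.** SAP 8.1.3, under CTC, plans two readouts (traditional and all-candidate cells), "each expressed as CTC/mL will be assessed in pre treatment (Screening, Cycle 1 Day 1" and at several post-treatment visits. The analysis is optional: "Analysis of the CTC endpoints may include absolute CTC" is how the list begins. The full list is "absolute CTC and fold-change from baseline (pretreatment) by patient and % change and mean fold-change by cohort". The section does not say which pre-treatment sample is the baseline. It also does not say whether the cohort % change is a mean of patient % changes or the change in the cohort mean.

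Three other places bear on zeros:

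- SAP 7, on missing values, says for safety, immune-response, pharmacokinetic, pharmacodynamic and immunogenicity data that "analyses and summaries will be based on data as observed and no explicit imputation will be applied". CTC is not named.
- SAP 7.2 gives the visible substitution rule for low immune assay values: "Titers below the assay detection limit will be assigned a value of one-half that limit". It covers titers.
- For the next endpoint in SAP 8.1.3, "MDSC levels will be presented per patient and per cohort by GMTs and GMFRs". CTC has no geometric summary.

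On the population, Protocol 4.1.1 criterion 14 requires of biochemical-relapse participants "No evidence by imaging (of any type) of metastatic involvement as follows". On the sample, a footnote to the Amendment 6 schedule of activities in the protocol says "Approximately 10 mL of blood will be collected for evaluation of circulating tumor cells by the central laboratory".

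**The concern.** A count can be zero, and a fold-change or % change from zero has no value. Two things follow for the ratio summaries.

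First, participants with a zero baseline cannot contribute. If CTC later appear in them, the cohort mean fold-change does not register it.

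Second, the participants who remain were kept because their baseline draw was positive. At low counts their next draw is lower on average, which is regression to the mean. At moderate counts the arithmetic mean of ratios errs the other way, because a chance-low denominator inflates a ratio more than a chance-high one shrinks it. The artefact therefore changes direction with the count level, and two cohorts with different CTC burden could appear to differ when neither has changed.

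Cohorts are non-randomised, have 15 to 20 participants each in Part B, and have no untreated comparator, so nothing inside the trial would expose a spurious shift.

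**Working it through.** The documents state no CTC figure, so there is nothing of the plan's own to reproduce.

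**Inputs from the documents.** Cohort sizes are 20 (1B), 15 (5B) and 18 (3B), from SAP 4.3. Cohorts 1B and 5B are biochemical relapse: 20 + 15 = 35. The draw is about 10 mL.

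**Assumed input.** The mean number of cells per sample, μ, is not in the documents and is shown over a range.

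**Model with no treatment effect.** Baseline X and follow-up Y are independent Poisson counts with the same mean μ. Participants with X = 0 are dropped from the ratio.

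- Proportion dropped: P(X = 0) = exp(−μ).
- Expected fold-change in the rest: E[Y/X | X ≥ 1] = μ × S / (1 − exp(−μ)), where S is the sum over k ≥ 1 of P(X = k)/k.

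Worked cases:

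- μ = 0.5: exp(−0.5) = 0.607 and S = 0.3458, so 0.5 × 0.3458 / 0.393 = 0.44.
- μ = 1: exp(−1) = 0.368 and S = 0.4848, so 1 × 0.4848 / 0.632 = 0.77.
- μ = 3: exp(−3) = 0.050 and S = 0.4111, so 3 × 0.4111 / 0.950 = 1.30.

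| μ (cells per sample) | Zero baselines | Expected dropped of 35 | Mean fold-change, no effect |
|---|---|---|---|
| 0.5 | 61% | 21.2 | 0.44 |
| 1 | 37% | 12.9 | 0.77 |
| 1.5 | 22% | 7.8 | 1.00 |
| 2 | 14% | 4.7 | 1.15 |
| 3 | 5% | 1.7 | 1.30 |
| 5 | 0.7% | 0.2 | 1.29 |
| 10 | about 0 | about 0 | 1.13 |
| 20 | about 0 | about 0 | 1.06 |

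Chance conversion from zero to positive is exp(−μ) × (1 − exp(−μ)): 0.607 × 0.393 = 24% of all participants at μ = 0.5, and 0.368 × 0.632 = 23% at μ = 1. None of these enter the ratio.

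**Between-patient variation.** If each participant has a stable mean drawn from a gamma distribution with shape 0.5, simulation under no effect gives a mean fold-change of 0.69 at an overall mean of 0.5 (71% zero baselines) and 0.88 at 1 (58% zeros). The fall is smaller, but more participants drop out.

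**% change.** As a mean of patient values it equals 100 × (mean fold-change − 1), so it has the same fault: −56% at μ = 0.5 and +30% at μ = 3. As a change in the mean over all participants, zeros kept, it is 0% under no effect.

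**Check of the alternatives under no effect.**

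- Geometric mean of (Y + 0.5)/(X + 0.5), all participants, single-sample baseline: 1.00 in every gamma-Poisson scenario run (shape 0.3 to 2, mean 0.5 to 20).
- The same offset with an arithmetic mean of ratios: 1.11 to 1.51 across those scenarios. The offset alone does not cure the bias.
- Geometric ratio against the average of the Screening and Cycle 1 Day 1 counts: 0.91, 0.89, 0.90 and 0.95 at Poisson means 0.5, 1, 2 and 5, and about 0.94 to 0.95 with gamma shape 0.5. The average is less variable than one draw and so has the higher expected log, which creates a spurious fall.
- Units: at 10 mL per sample, an offset of 0.5 CTC/mL equals 0.5 × 10 = 5 cells, ten times an offset of 0.5 cells.

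**The case against.** Several points on the other side stand.

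- The analysis is optional, and absolute CTC by patient is listed with the ratios. SAP 8.1.3 also allows plots of individual CTC trends. A reader might infer that conversions from zero are lost from the CTC analysis altogether. The documents do not support that: they are lost only from the ratio summaries.
- A reader might take SAP 7 as forbidding any treatment of zeros. It does not. It concerns missing values, a zero count is observed, and CTC is not named. The gap is that no zero-baseline rule is visible.
- SAP text is redacted between 6.5 and 6.7, at the start of section 7, and between 8.1.3 and 8.1.5. A rule could sit there. The visible CTC paragraph refers to none.
- A reader might conclude that the plan will show a CTC fall for an inert treatment. That needs low counts, and the documents give no count distribution for either readout. The bias is about nil near 1.5 cells per sample, upward at 3 and about 6% at 20. The 56% fall belongs to identical patients at a mean of 0.5.
- If the cohort % change means change in the all-participant mean, that measure is sound.

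None of this rescues the cohort mean fold-change, which is undefined at zero and, apart from a crossover near 1.5 cells, is off 1 under no effect across the Poisson range examined.

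**Conclusion.** The point holds as a minor one. Patient fold-change and patient-level % change have no value at a zero baseline, no visible rule covers it, and the arithmetic mean fold-change in the remaining participants is a biased summary of no change. Under Poisson counts it runs from 0.44 (mean 0.5) through 1.0 (mean 1.5) to 1.30 (mean 3) and back to 1.06 (mean 20).

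The undefined ratio is a matter of arithmetic. The share of participants affected, and the direction and size of the bias, rest on assumed count distributions. That zeros are plausible in the 35 biochemical-relapse participants is inferred from their having no detectable metastases, not from CTC data. No hypothesis is tested on CTC. The effect is confined to how an optional descriptive table would be read, and the primary safety conclusion does not depend on it.

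**What to change.** In SAP 8.1.3, replace the CTC cohort mean fold-change and the mean of patient % changes with:

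1. A shift table of undetectable versus detectable CTC, baseline against each visit, for all participants with both samples.
2. The geometric mean ratio of (count per sample + 0.5), follow-up to baseline, with the offset applied to cells per sample and not to CTC/mL.

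Name one pre-treatment sample as baseline for the ratio, for example Cycle 1 Day 1, or Screening if that is missing. Do not average the two against a single follow-up draw. If a cohort % change is kept, define it as the change in the mean over all participants with both samples, zeros included. Absolute CTC by patient can stay as it is.

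The cost is SAP wording and one table, plus having the cell count or the assayed volume in the data so that CTC/mL can be converted. The downside is that the 0.5 offset is a convention.
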